12.4.5 Sensitivity analyses

Given the descriptive nature of the summary of primary safety endpoints, no sensitivity analysis is planned.

Supplementary analysis 12.4.6

Subgroup analyses

Subgroup analyses will be performed on the primary endpoints based on the participant's baseline status:

Age

As the sample size is small, data will be only summarized within each subgroup. Analysis supporting secondary objectives

The secondary objective is:

To evaluate the efficacy of IV OAV101 at 6, 12, and 18 months post-infusion in participants with SMA weighing ≤ 17 kg, as measured by the following:

WHO-MGRS

All secondary efficacy endpoints will be analyzed for the FAS.

12.4.7 Efficacy and/or Pharmacodynamic endpoint(s)

The number and proportion of participants achieving each WHO developmental milestone will be presented at 6-, 12-, and 18- months post-infusion.

The analysis will take into account the following intercurrent events using a composite strategy:

- Intake of prohibited concomitant medications
- Discontinuation from study due to reasons other than death

This means that if the any of the intercurrent events of interest occur the participant will be regarded as a non-responder from when the first intercurrent event of interest occurs.

12.4.8 Safety endpoints

For all safety analyses, the Safety set will be used.

The overall observation period will be divided into two mutually exclusive segments:

- 1. Pre-treatment period: from day of participant's informed consent to the day before infusion of OAV101
- 2. On-treatment period: from day of infusion of OAV101 through to the last study visit.

Adverse events

Details of the summary of AEs for the primary endpoint are detailed in Section 12.4.

In addition, separate summaries will be provided for death and other significant TEAEs leading to discontinuation.

All AEs, deaths, and SAEs (including those from the pre-treatment period) will be listed and those collected during the pre-treatment period will be flagged.

Vital signs

Details of the summary of AEs for the primary endpoint are detailed in Section 12.4.

12-lead ECG

Details of the summary of 12-lead ECG (cardiac safety assessment) for the primary endpoint are detailed in Section 12.4

- 1. PR, QRS, QT, QTcF, and RR intervals will be obtained from 12-lead ECGs for each participant during the study. ECG data will be read and interpreted (locally).
- 2. Categorical Analysis of QT/QTc interval data based on the number of participants meeting or exceeding predefined limits in terms of absolute QT/QTc intervals or changes from baseline will be presented.

All ECG data will be summarized by visit/timepoint.

Clinical laboratory results

Details of the summary of clinical laboratory results for the primary endpoint are detailed in Section 12.4.

In addition, shift tables using the low/normal/high/ (low and high) classification will be used to compare baseline to the worst on-treatment value.

Grading of laboratory values will be assigned programmatically as per NCI CTCAE version 4.03. The calculation of CTCAE grades will be based on the observed laboratory values only, clinical assessments will not be taken into account.

CTCAE Grade 0 will be assigned for all non-missing values not graded as 1 or higher. Grade 5 will not be used.

For laboratory tests where grades are not defined by CTCAE version 4.03, results will be categorized as low/normal/high based on laboratory normal ranges.

The following listings/summaries will be generated separately for hematology, and biochemistry tests:

• Listing of all laboratory data with values flagged to show the corresponding CTCAE version 4.03 grades if applicable and the classifications relative to the laboratory normal ranges

For laboratory tests where grades are defined by CTCAE version 4.03:

- Worst post-baseline CTCAE grade (regardless of the baseline status). Each participant will be counted only once for the worst grade observed post-baseline.
- Shift tables using CTCAE version 4.03 grades to compare baseline to the worst ontreatment value

[figure not shown]
For laboratory tests where grades are not defined by CTCAE version 4.03:

• Shift tables using the low/normal/high/ (low and high) classification to compare baseline to the worst on-treatment value.

Other safety evaluations

Details of the summary of echocardiogram (cardiac safety assessment) for the primary endpoint are detailed in Section 12.4.

12.6 Interim analyses

An interim analysis will be performed once the last participant reaches the 6 and 12-month time point and will include all available data up until that data cut-off. The interim analysis is intended to provide an early safety readout from the study. No study design change or adaptation will be implemented based on the outcome of the interim analysis.

12.7 Sample size calculation

12.7.1 Primary endpoint(s)

There is no formal sample size calculation performed for this study. The primary objective is to evaluate descriptively the safety and tolerability of IV OAV101 over a 18 month post infusion period in participants with SMA weighing equal or less than 17kg. No hypothesis testing will be performed.

The sample size is based on recruitment estimatives and clinical drug availability. Based on this assumption, it is anticipated that approximately 15 participants will be enrolled in this study. From a medical perspective, this number is considered reasonable to provide descriptive safety information.

If the true incidence rate of an AE is 14%, then the probability of seeing at least one AE with a sample size of 15 participants is approximately 90%.

13 Ethical considerations and administrative procedures

13.1 Regulatory and ethical compliance

This clinical study was designed and shall be implemented, executed and reported in accordance with the ICH Harmonized Tripartite Guidelines for GCP, with applicable local regulations (including European Directive 2001/20/EC, US CFR 21), and with the ethical principles laid down in the Declaration of Helsinki.

13.2 Responsibilities of the investigator and IRB/IEC

Before initiating a trial, the Investigator/institution must obtain approval/favorable opinion from the IRB/IEC for the trial protocol, written informed consent form, consent form updates, participant recruitment procedures (eg, advertisements) and any other written information to be provided to participants. Prior to study start, the Investigator is required to sign a protocol

signature page confirming his/her agreement to conduct the study in accordance with these documents and all of the instructions and procedures found in this protocol and to give access to all relevant data and records to Novartis monitors, auditors, Novartis Quality Assurance representatives, designated agents of Novartis, IRBs/IECs, and regulatory authorities as required. If an inspection of the clinical site is requested by a regulatory authority, the Investigator must inform Novartis immediately that this request has been made.

13.3 Publication of study protocol and results

The protocol will be registered in a publicly accessible database such as clinicaltrials.gov and as required in EudraCT. In addition, after study completion (defined as last participant last visit) and finalization of the study report the results of this trial will be submitted for publication and posted in a publicly accessible database of clinical trial results, such as the Novartis clinical trial results website and all required Health Authority websites (eg clinicaltrials.gov, EudraCT etc.).

For details on the Novartis publication policy including authorship criteria, please refer to the Novartis publication policy training materials that were provided to you at the trial Investigator meetings.

13.4 Quality Control and Quality Assurance

Novartis maintains a robust QMS that includes all activities involved in quality assurance and quality control, to ensure compliance with written SOPs as well as applicable global/local GCP regulations and ICH Guidelines.

Audits of Investigator sites, vendors, and Novartis systems are performed by auditors, independent from those involved in conducting, monitoring or performing quality control of the clinical trial. The clinical audit process uses a knowledge/risk based approach.

Audits are conducted to assess GCP compliance with global and local regulatory requirements, protocols and internal SOPs, and are performed according to written Novartis processes.

14 Protocol adherence

This protocol defines the study objectives, the study procedures and the data to be collected on study participants. Additional assessments required to ensure safety of participants should be administered as deemed necessary on a case by case basis. Under no circumstances including incidental collection is an Investigator allowed to collect additional data or conduct any additional procedures for any purpose involving any investigational drugs under the protocol, other than the purpose of the study. If despite this interdiction prohibition, data, information, observation would be incidentally collected, the Investigator shall immediately disclose it to Novartis and not use it for any purpose other than the study, except for the appropriate monitoring on study participants.

Investigators ascertain they will apply due diligence to avoid protocol deviations. If an Investigator feels a protocol deviation would improve the conduct of the study this must be considered a protocol amendment, and unless such an amendment is agreed upon by Novartis and approved by the IRB/IEC and Health Authorities, where required, it cannot be implemented.

16.1 Appendix

Appendix 1: Clinically notable laboratory values and vital signs

Appendix 2: Liver monitoring guidelines

Appendix 3. Performance criteria for World Health Organization (WHO) developmental milestones

16.1.1 Clinically notable laboratory values and vital signs

Clinically relevant laboratory abnormalities

Age-appropriate, normal laboratory values and clinical measurements should be used in pediatric population. Laboratory tests are commonly interpreted in relation to established reference intervals. These limits serve to differentiate between normal and pathological findings, and to gauge the severity of any abnormal increases or decreases. As far as laboratory parameters are known to characteristically vary with age, pediatric test results are usually interpreted in relation to these physiological dynamics. Reference intervals for pediatric patients have been calculated by partitioning data from a healthy reference population into age groups, so that the corresponding subset-specific percentiles would form step functions of age (Hirschmann et al 2017).

Vital signs

Within vital signs data, height and weight are commonly collected along with heart rate, respiratory rate, and blood pressure. The exam and vital sign data can be interpreted only with a thorough understanding of normal values. In pediatrics, normal respiratory rate, heart rate, and blood pressure have age-specific norms.

Vital sign Value		Patient age at visit		
		< 18 ye	ears	≥ 18 years
Systolic blood pressure (mmHg)	High		percentile age and group¹	≥ 180 with increase from updated baseline ⁵ or ≥ 20 mmHg
	Low	≤ 5 th pe the age height		≤ 90 with decrease from updated baseline ⁵ or ≥ 20 mmHg
Diastolic blood pressure (mmHg)	High		percentile age and group¹	≥ 105 with increase from updated baseline ⁵ or ≥ 15 mmHg
	Low	≤ 5 th pe the age height		≤ 50 with decrease from updated baseline ⁵ or ≥ 15 mmHg
	High	≥ 38.4		≥ 39.1

Oral body temperature (°C)	Low		≤ 35.0	≤ 35.0
Pulse rate (bpm) ²	High	12-18 months	> 140	≥ 120 with
		18-24 hours	> 135	increase from
		2-3 years	> 128	updated baseline ⁵ or ≥ 15 mmHg
		3-4 years	> 123	
		4-6 years	> 117	
		6-8 years	> 111	1
		8-12 years	> 103	1
		12-15 years	> 96	1
		≥ 15 years	> 92	1
	Low	12-18 months	< 103	≤ 50 with
		18-24 hours	< 98	decrease from
		2-3 years	< 92	updated baseline ⁵ or ≥ 15 mmHg
		3-4 years	< 86	_ or _ ro mining
		4-6 years	< 81	1
		6-8 years	< 74	1
		8-12 years	< 67	
		12-15 years	< 62	1
		≥ 15 years	< 58	1
Weight	High		Increase from baseline³ of ≥ 2 BMI-for-age percentile cetagories⁴	Weight increase from updated baseline ⁵ of ≥ 10%
	Low		Decrease from baseline³ of ≥ 2 BMI-for-age percentile cetagories⁴	Weight decrease from updated baseline ⁵ of ≥ 10%
Respiratory rate	High	12-18 months	> 46	≥ 30
(breath per		18-24 hours	> 40	
minutes) ²		2-3 years	> 34	
		3-4 years	> 29	
		4-6 years	> 27	
		6-8 years	> 24	7
		8-12 years	> 22	7
		12-15 years	> 21	
		≥ 15 years	> 20	7
	Low	12-18 months	< 28	≤ 10
		18-24 hours	< 25	7
		2-3 years	< 22	7
		3-4 years	< 21	7

	4-6 years	< 20	
	6-8 years	< 18	
	8-12 years	< 16	
	12-15 years	< 15	
	≥ 15 years	< 13	

bpm=beats per minute

	ALT > 3 x ULN	Normal or elevated	Severe fatigue, nausea, vomiting, right upper quadrant pain	 Initiate close monitoring (hospitalizatio n when appropriate) and workup for competing etiologies^a Exclude underlying liver disease Detailed history of
				concomitant medications (e.g acetaminoph en) Consult pediatric Gastroenterol ogist ^b

^a Work-up for competing etiologies may include (but not limited to) viral Hepatitis Panel (IgM anti-HAV; HBsAg, IgM anti-HBc, HBV DNA; anti-HCV, HCV RNA, IgM & IgG anti-HEV, HEV RNA), Viral panel (CMV, EBV, HSV), autoimmune hepatitis (ANA, ASMA titers)

^bConsider appropriate imaging and liver biopsy in consultation with Pediatric Gastroenterologist

Table 16-3 Follow up requirements for liver laboratory triggers - isolated hyperbilirubinemia

Criteria	Actions required	Follow-up monitoring
Total Bilirubin(isolated)		
>1.5 – 3.0 ULN	Repeat LFTs within 48-72 hours	Monitor LFTs weekly until resolution to ≤ Grade 1 or to baseline
> 3 - 10 × ULN (in the absence of known Gilbert syndrome)	 Repeat LFT within 48-72 hours Hospitalize if clinically appropriate Establish causality Record the AE and contributing factors (e.g. conmeds, med hx, lab) in the appropriate CRF 	Monitor LFTs weekly until resolution to ≤ Grade 1 or to baseline (ALT, AST, total bilirubin, Alb, PT/INR) Test for hemolysis (e.g. reticulocytes, haptoglobin, unconjugated [indirect] bilirubin)
> 10 x ULN	 Hospitalize the participant Establish causality Record the AE and contributing factors(e.g. conmeds, med hx, lab)in the appropriate CRF 	ALT, AST, total bilirubin, Alb, PT/INR, until resolution (frequency at investigator discretion)
Any AE potentially indicative of a liver toxicity	 Hospitalization if clinically appropriate Establish causality Record the AE and contributing factors(e.g., conmeds, med hx, lab)in the appropriate CRF 	Investigator discretion

Based on investigator's discretion investigation(s) for contributing factors for the liver event can include: Serology tests, imaging and pathology assessments, pediatric gastroenterologist or hepatologist's consultancy; obtaining more detailed history of symptoms and prior or concurrent diseases, history of concomitant drug use, exclusion of underlying liver disease.

16.1.3 Performance criteria For World Health Organization (WHO) developmental motor milestones

Gross Motor Milestone	Performance Criteria	
Sitting without support	Child sits up straight with the head erect for at least 10 seconds. Child does not use arms or hands to balance body or support position.	
Hands-and-knees crawling	Child alternately moves forward or backward on hands and knees. The stomach does not touch the supporting surface.	
	There are continuous and consecutive movements, at least 3 in a row.	

Standing with assistance	Child stands in upright position on both feet, holding onto a stable object (eg, furniture) with both hands without leaning on it.
	The body does not touch the stable object, and the legs support most of the body weight.
	Child thus stands with assistance for at least 10 seconds.
Walking with assistance	Child is in upright position with the back straight.
	Child makes sideways or forward steps by holding onto a stable object (eg, furniture) with 1 or both hands.
	One leg moves forward while the other supports part of the body weight. Child takes at least 5 steps in this manner.
Standing alone	Child stands in upright position on both feet (not on the toes) with the back straight.
	The legs support 100% of the child's weight. There is no contact with a person or object. Child stands alone for at least 10 seconds.
Walking alone	Child takes at least 5 steps independently in upright position with the back straight.
	One leg moves forward while the other supports most of the body weight. There is no contact with a person or object.

WHO = World Health Organization

Source: World Health Organization Multicentre Growth Reference Trial Group (WHO 2006)

1. ABBREVIATIONS

AE	Adverse event
AESI	Adverse event of special interest
ALT	Alanine aminotransferase
AST	Aspartate aminotransferase
ATC	Anatomical Therapeutical Chemical
BLQ	Below limit of quantification
ВМІ	Body Max Index
CRF	Case report form
CTCAE	Common Toxicity grading Adverse event
DMC	Data monitoring committee
eCRF	Electronic Case Report Form
ENR	Patient Enrolled Set
EOS	End of study
FAS	Full Analysis Set
PRO	Patient reported outcome
PT	Preferred term
ROM	Range of motion
SAE	Serious adverse event
SAF	Safety analysis set
SAP	Statistical analysis plan
SMA	Spinal muscular atrophy
SOC	System Organ Class
TEAE	Treatment Emergent Adverse Event
TLF	Tables, Listings, and Figures
D	Decrease where the condition

Document: Document path and title

Template No.: RWI_TP_BIOS0013 Revision 2 Reference: RWI_WI_BIOS0015

Page 7 of 45

TOD	Target organ damage
TTNT	Time to next treatment
ULQ	upper limit of quantification
WHO-MGRS	World Health Organization Multicenter Growth Reference Study

Document: Document path and title

Template No.: RWI_TP_BIOS0013 Revision 2 Reference: RWI_WI_BIOS0015

Page 8 of 45

2. INTRODUCTION

This statistical analysis plan (SAP) describes the rules and conventions to be used in the presentation and analysis of effectiveness and safety of OAV101 (AVXS-101) in pediatric patients with spinal muscular atrophy (SMA). It describes the data to be summarized and analyzed, including specifics of the statistical analyses to be performed.

This statistical analysis plan (SAP) is based on protocol version 0.0 dated 20 July 2021and amendment 1.0 dated 24 March 2022 and Case Report Forms (CRFs) version 1.1 dated 20 January 2022.

3. STUDY OBJECTIVES

3.1 Primary Objectives

To assess the safety and tolerability of IV OAV101 over an 18-months post-infusion period in participants with SMA weighing to \leq 17 kg.

3.2 Secondary Objectives

The secondary objective is:

To evaluate the efficacy of IV OAV101 at 6-, 12-, and 18-months post-infusion in participants with SMA weighing ≤ 17 kg, as measured by the following:

• World Health Organization-Multicenter Growth Reference Study (WHO-MGRS)

Document: Document path and title

Template No.: RWI_TP_BIOS0013 Revision 2 Reference: RWI_WI_BIOS0015

Page 9 of 45

4. STUDY DESIGN

4.1 General Description

This is an open-label, single arm, multi-center study to evaluate the safety, tolerability, and efficacy of IV OAV101 in symptomatic SMA pediatric participants. The study will enroll participants that weigh \leq 17 kg.

Participants who meet eligibility criteria at Screening and Baseline visits will receive a single dose of IV OAV101 on Day 1 (Treatment period) at the approved dose of 1.1e14 vg/kg and will be followed for a period of 18 months. The study will include a 20-day screening period in which there will be 2 Screening visits, during which, eligibility will be assessed (Screening 1), weight will be collected for dose calculation (Screening 2), and baseline assessments will be performed prior to treatment. For the study duration, participants will be completing visits as defined in the Schedule of Assessments. On Day -1, participants will be admitted to the hospital for pretreatment baseline procedures including prednisolone treatment per study protocol. On Day 1, participants will receive a single IV infusion of OAV101. Participants may be discharged 12-48 hours after the infusion, based on Investigator judgment.

Safety monitoring will be performed on an ongoing basis per protocol requirement and will be evaluated by the clinical safety team as well as DMC. An interim analysis for safety and efficacy will be performed once the last participant completes 6-months of follow-up and will include all available data up until that data cut-off. Final analysis will be planned once all participants have completed Month 18 End of Study (EOS) assessments.

After study completion eligible participants will be invited to enroll into RESTORE registry study to collect additional safety and efficacy data.

4.2 Schedule of Events

The schedule of events can be found in *Section 8. Visit schedule and assessments* of the protocol.

Document: Document path and title

Template No.: RWI_TP_BIOS0013 Revision 2 Reference: RWI_WI_BIOS0015

4.3 Changes to Analysis from Protocol

Not applicable.

5. PLANNED ANALYSES

- 1. Two interim analyses
- 2. Final analysis

5.1 Interim Analyses

The interim analyses are intended to provide an early safety readout from the study. No study design change or adaptation will be implemented based on the outcome of the interim analyses. The interim analyses will be performed once the last participant reaches the 6-months (week 26) and 12-month (week 52) time point and will include all available data up until that data cut-off. See section 12.6 Interim analyses of the protocol for more details.

Derivations and definitions for the interim analyses will be based on those required for the final analysis contained in this analysis plan unless deviations are stated within the text. The list of outputs provided with the full set of output templates (planned for the final analysis) will highlight which of these outputs will also be provided for the interim analyses.

5.2 Final Analysis

All final, planned analyses identified in this SAP will be performed by Biostatistics following Client Authorization of this Statistical Analysis Plan.

6. ANALYSIS SETS

6.1 All Patients Enrolled Set [ENR]

The all Patients enrolled (ENR) set will contain all Patients who provide informed consent for this study.

Document: Document path and title

Template No.: RWI_TP_BIOS0013 Revision 2 Reference: RWI_WI_BIOS0015

Page 11 of 45

6.2 Full Analysis Set [FAS]

The full analysis set (FAS) will contain all enrolled patients who received the study medication. The same set will be considered for the safety analysis set (SAF).

7. GENERAL CONSIDERATIONS

The overall observation period will be divided into two mutually exclusive segments:

- 1. Pre-treatment period: from day of participant's informed consent to the day before infusion of OAV101
- 2. On-treatment period: from day of infusion of OAV101 through to the last study visit.

7.1 Reference Start Date

Reference start date is defined as the day of the study medication dosing (Day 1) and will appear in every listing where an assessment date or event date appears.

7.2 Baseline

Baseline is defined as the last non-missing measurements taken prior to reference start date (including unscheduled assessments) and after the study enrollment.

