8.2.3 Physical examination

Physical examinations will be conducted by the Investigator or designee as specified in the Table 8-1. The Day 1 physical examination will be performed prior to the start of gene replacement therapy infusion. Physical examinations include a review of the following systems: (HEENT), lungs/thorax, cardiovascular, abdomen, musculoskeletal, neurologic, dermatologic, lymphatic, and genitourinary.

Physical examination data will be captured on source documentation.

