8.4.3 Vital signs

Vital sign parameters include blood pressure, respiratory rate, pulse, temperature, and oxygen saturation level. Vital signs will be obtained as specified in the Table 8-1. On Day 1, vital signs will be recorded pre-dose and then monitored as specified in the Table 8-1.

Height and weight will be measured (supine or standing) at each study visit. Screening weight shall be obtained \leq 14 days prior to Day 1. On Day 1, weight and height will be measured predose.

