15. PRIMARY OUTCOMES

15.1 Safety Outcome

All outputs for primary outcomes will be based on the FAS.

The primary outcomes are related to the safety assessments:

- Evaluation of treatment emergent AEs and SAEs
- Evaluation of important identified and potential risks
- Evaluate changes from baseline in vital signs, cardiac safety assessments, and clinical laboratory results

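### The SAP splits baseline from on-treatment by calendar day, so Day 1 readings that the protocol requires before infusion cannot be baseline and are dated on-treatment

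*SAP*

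**What the plan says.** **Baseline.** SAP 7.1 sets the reference start date as the day of dosing, Day 1. SAP 7.2 then says: "Baseline is defined as the last non-missing measurements taken prior to reference start date". Unscheduled values count, provided that they follow enrollment.

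**Periods.** SAP 7 defines two segments that do not overlap: "Pre-treatment period: from day of participant's informed consent to the day before infusion of OAV101" and "On-treatment period: from day of infusion of OAV101 through to the last study visit". Protocol 12.4.8 has the same split.

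**Day 1 measurements.** Protocol 8.4.3 says "On Day 1, vital signs will be recorded pre-dose and then monitored as specified in the Table 8-1" and "On Day 1, weight and height will be measured predose". Protocol 8.2.3 adds: "The Day 1 physical examination will be performed prior to the start of gene replacement therapy infusion".

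**Use in the analysis.** SAP 15.1 lists as a primary outcome: "Evaluate changes from baseline in vital signs, cardiac safety assessments, and clinical laboratory results". SAP 15.4 counts weight, height and BMI among the vital signs. It promises actual values and change from baseline by visit, and the incidence of abnormal values. SAP Table 1 lists Baseline (Day -1) and Day 1 as separate analysis visits.

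**The concern.** A value taken before exposure should not be labelled on-treatment. Here the label follows from the stated rule, because neither document has a clock-time criterion or an exception for pre-dose records.

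Two things follow for a primary outcome. First, the Day 1 change in weight, height and BMI contains no post-exposure information. Second, Day 1 is the visit row where an acute infusion effect on pulse, blood pressure, respiration, temperature or oxygen saturation should show, and the SAP does not say which Day 1 reading enters it. Two programmers could produce different Day 1 tables from the same data, and one of them could consist only of pre-infusion readings.

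**Working it through.** **The plan's own figure.** The only probability stated is in protocol 12.7.1: about a 90% chance of at least one AE among 15 participants at a true rate of 14%. 1 - 0.86^15 = 0.896, so it reproduces. This point does not depend on it.

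**Applying the rule.** Under SAP 7.1 and 7.2 a record is baseline-eligible if its date is before Day 1. Under SAP 7 it is on-treatment if its date is Day 1 or later.

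| Day 1 record required before infusion | Source | Date before Day 1? | On-treatment? |
|---|---|---|---|
| Vital signs | Protocol 8.4.3 | No | Yes |
| Weight and height (hence BMI) | Protocol 8.4.3 | No | Yes |
| Physical examination | Protocol 8.2.3 | No | Yes |

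**What fills the Day 1 row.**
- Weight, height, BMI: Day 1 pre-dose minus the last earlier value, normally Day -1. Both are pre-exposure.
- Other vital signs: protocol 8.4.3 points to Table 8-1 for monitoring after the pre-dose reading, but Table 8-1 has a single Day 1 mark with no post-dose times. Protocol 6.7 adds continuous monitoring during infusion. Several Day 1 readings can therefore exist, and the SAP text selects none. The output templates in SAP Appendix 3 are not in the public document, so a selection rule there cannot be excluded.

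**Reach, from Table 8-1.**
- Vital signs are scheduled on Day 1 and at 13 later visits (Days 2 and 3; Weeks 1, 2, 3, 4, 6, 8, 10, 12, 26, 52, 78). The affected row is 1 of 14.
- Hematology, chemistry, troponin, ECG, echocardiogram and the milestone checklist have no Day 1 mark, so their scheduled baselines are unaffected.
- Vital signs, weight, height and physical examination all have a Day -1 mark. Baseline exists; it is one day older than the last pre-exposure value.

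**How far a misdated abnormal reading could move the incidence of abnormal values.** The documents give no pre-dose abnormality rate, so take q = 5%, 10% or 20% as an assumption. The 10% case matches the 5th and 95th percentile limits for one blood-pressure measure (SAP Table 3) if these children resemble the reference population.

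- Expected pre-dose flags among 15 children, 15q: 0.75, 1.5, 3.
- Chance of at least one, 1 - (1-q)^15: 54%, 79%, 96%.
- Suppose instead that each child is counted once over all visits, and that visits are independent (a further assumption). The pre-dose reading then adds (1-q)^13 - (1-q)^14 = q(1-q)^13 to a child's chance of any flag: 2.6, 2.5 and 1.1 percentage points. At q = 10% this is 1 - 0.9^13 = 74.6% rising to 1 - 0.9^14 = 77.1%. Correlation between a child's readings would change these figures.

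**The case against.** The strongest reply is that Day -1 is the designed baseline. Table 8-1 and SAP Table 1 both give it that name, and protocol section 3 places the pre-treatment baseline procedures there. The treatment of interest in protocol 2.1 includes the corticosteroid started 24 hours before infusion, and protocol 4.5 lists raised blood pressure among reported corticosteroid effects. A Day 1 pre-dose baseline would absorb any early steroid effect, while Day -1 sits closer to the start of the strategy under study. The documents do not say whether Day -1 readings precede the first steroid dose. This stands as a defence of Day -1 as baseline. It does not make a pre-infusion Day 1 reading on-treatment, nor does it say which Day 1 reading is summarised.

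It also stands that the study is descriptive, without hypothesis tests, and that acute reactions are captured by other routes: continuous monitoring and AE observation (protocol 6.7), and treatment-emergent events, which protocol 12.4.2 defines as following the infusion.

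Three stronger readings are tempting and not supported:

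- *A true Day 1 change is halved.* This needs one pre-dose and one post-dose reading to be averaged. No section describes averaging or pooling.
- *The 79% chance of at least one pre-dose flag measures the harm.* Percentile limits flag reference children at every visit, whatever the baseline rule. Over all visits the added chance per child is only a few points. SAP 15.4 also does not restrict the incidence of abnormal values to the on-treatment period, so attribution to OAV101 is an inference.
- *All change-from-baseline safety endpoints are affected.* Table 8-1 rules this out for scheduled laboratory and cardiac assessments.

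**Conclusion.** The point holds within these limits. By the SAP's wording, every Day 1 vital sign, weight, height (hence BMI) and physical examination taken before infusion is barred from baseline and dated on-treatment, for all of about 15 participants. The Day 1 change for weight, height and BMI is uninformative, and the Day 1 vital-signs row is undefined and may be pre-dose. This follows from the text and needs no numerical assumption.

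The size is modest: one visit row in a primary outcome, with a Day -1 baseline available throughout. The documents do not allow any dilution of an infusion effect to be quantified. The point should be corrected because it is a misclassification written into the rules and is cheap to remove. It does not threaten the study's overall safety conclusions.

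**What to change.** 1. SAP 7: treat Day 1 records taken before the start of infusion as pre-treatment, by recorded time or pre-dose label, and add a rule for missing times.
2. SAP 7.2: define baseline as the last non-missing value before the start of infusion. If the sponsor prefers Day -1 because of the steroid, say so and give the reason; item 1 still applies.
3. SAP 7.4 and 15.4: name the reading, taken after the infusion has started, that fills the Day 1 vital-signs row. Drop the Day 1 change for weight, height and BMI.
4. Align the period definitions in protocol 12.4.8, or record the departure in SAP 4.3, which now reports no changes from the protocol.
5. Confirm that the eCRF captures a time or pre-dose label for Day 1 measurements. The documents imply this but do not state it.

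The cost is wording in the SAP, and in the protocol if it is aligned. No new data are needed if item 5 is confirmed. The one drawback is that a Day 1 pre-dose baseline falls after the first steroid dose, so any early steroid effect enters baseline instead of the change.
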